2.2 Amgen Investigational Product Background

Darbepoetin alfa, an ESA with 2 more consensus N-linked carbohydrate addition sites than rHuEpo, has a longer mean residence time and a 3-fold longer serum half-life than rHuEpo in both dialysis and cancer patients as well as demonstrating augmented in vivo activity (Egrie et al, 2003; Elliott et al, 2004; Jung and Schwartz, 2002;

Macdougall et al, 1999) and hence may afford patients convenience in dosing schedules. Darbepoetin alfa is manufactured by recombinant DNA technology using a Chinese hamster ovary mammalian cell line. Darbepoetin alfa was initially approved for the treatment of symptomatic anemia associated with chronic renal failure in patients receiving dialysis as well as patients not on dialysis. Darbepoetin alfa was subsequently approved for the treatment of symptomatic anemia in patients with nonmyeloid malignancy receiving chemotherapy in the European Union and is approved for use in the oncology setting in multiple countries, including the United States, Australia, and Canada.

Several studies have evaluated the use of darbepoetin alfa in anaemic patients with MDS (Gabrilove et al, 2008; Gotlib et al, 2009; Mannone et al, 2006; Moyo et al, 2008; Musto et al, 2005; Park et al, 2008; Patton et al, 2005; Stasi et al, 2005; Villani et al, 2007; Villegas et al, 2011). Some studies evaluated darbepoetin alfa in combination with G-CSF (ie, filgrastim, pegfilgrastim) to address the potential of a synergistic response (Mannone et al, 2006; Park et al, 2008). In all of these studies, efficacy was primarily determined by erythroid response. Unless otherwise noted, an erythroid response was determined using the IWG definitions of major and minor response published in 2000. Several of the studies categorised patients by risk of progression to AML (Gabrilove et al, 2008; Mannone et al, 2006; Park et al, 2006; Park et al, 2008; Villani et al, 2007; Villegas et al, 2011). These prognostic categorisations were derived from the IPSS.

The overall response rate in these trials ranged from 20% to 74%. Response rates were higher in patients with no prior ESA exposure as well as those with baseline endogenous erythropoietin levels below 500 U/L. While the number of subjects in most of the studies was small, the largest included more than 200 subjects.

Page 23 of 66

Meta-analysis of Darbepoetin alfa Versus Epoetin alfa

Moyo et al (2008) conducted a meta-analysis of 30 clinical studies published from 1990 to 2006 that evaluated the effectiveness of darbepoetin alfa (8 studies [n = 389 evaluable]) or epoetin alfa (22 studies [n = 925 evaluable]) monotherapy for the treatment of patients with MDS related anaemia. This meta-analysis included data from randomised controlled studies as well as single-arm clinical studies and retrospective studies. The objectives of the meta-analysis were to assess erythroid response rates in studies that either did or did not use the IWG definition of response, identify predictors of response, and compare erythroid response rates for the 2 ESAs when adjusted for IWG criteria.

Baseline characteristics of the patients were similar in both the darbepoetin alfa and epoetin alfa studies that used IWG criteria to evaluate response. No significant differences were observed with respect to age, gender, proportion of patients with RA or RARS, transfusion dependency rates, or mean baseline haemoglobin; however, mean baseline serum erythropoietin was significantly lower among darbepoetin alfa-treated patients than among epoetin alfa-treated patients (P = 0.003).

The average initial weekly dose of darbepoetin alfa was 176 μ g (range: 100 to 315 μ g). Among patients who were treated in studies that used the IWG criteria to evaluate response, the pooled estimate of erythroid response among the darbepoetin alfa-treated patients was 59.4% (95% confidence interval [CI]: 49.0 to 69.9), which was not significantly different from the 57.6% (95% CI: 45.1 to 70.0) response rate among patients treated with epoetin alfa (*P* = 0.8282). The dose of darbepoetin alfa was positively correlated with increased erythroid response rates. A response rate of 71.1% was achieved across 235 patients receiving darbepoetin alfa between 166 and 300 μ g once weekly (QW). This was significantly greater than the response rate of 52.6% across the 154 patients who received darbepoetin alfa between 100 and 150 μ g QW (*P* < 0.001).

Refer to the specific section of the Darbepoetin alfa Investigator's Brochure for additional information related to the physical, chemical, and pharmaceutical properties and formulation.

2.3 Rationale

The rationale of this study is to provide required access to investigational product (IP; darbepoetin alfa) beyond the end of active treatment period of the darbepoetin alfa

amgen'

Page 24 of 66

MDS 20090160 study for subjects that continue to benefit from darbepoetin alfa treatment and to describe the safety of longer-term use in this patient population.

The MDS 20090160 study is a phase 3, multicenter, randomised, double-blind, placebo-controlled trial of darbepoetin alfa 500 µg administered Q3W to approximately 180 low or intermediate-1 risk anaemic MDS subjects. The 20090160 study consists of a 3-week screening period, 24-week double-blind treatment period, 48-week active treatment period, and long-term follow-up (LTFU) period.

2.4 Clinical Hypotheses

A formal statistical hypothesis will not be tested. Treatment emergent adverse events, progression to AML, and death will be summarized.

3. EXPERIMENTAL PLAN

3.1 Study Design

This is a phase 3b, multi-center, open-label, single-arm companion study to the phase 3 MDS 20090160 study for the treatment of anaemic subjects with MDS. Subjects that complete the active-treatment period of the darbepoetin alfa MDS 20090160 study and meet the eligibility criteria may be enrolled into this study to continue treatment of darbepoetin alfa for up to 73 weeks or until lack of response to IP, diagnosis of new malignancy, or progression to AML, whichever occurs first. The overall study design is described by a study schema at the end of the protocol synopsis section.

The study endpoints are defined in Section 10.1.1.

3.2 Number of Sites

Approximately 50 sites in Europe are expected to participate in the parent darbepoetin alfa MDS study (20090160). The total number of sites that may participate in this companion study is not known at this time; however, a minimum of 1 site will participate.

3.3 Number of Subjects

Participants in this clinical investigation shall be referred to as "subjects."

It is estimated that approximately 20% of the subjects that complete the double-blind treatment and active treatment periods of the parent study (20090160) may be eligible to enroll; however, not all subjects may consent, nor will the majority of sites participate in the companion study.

This is a companion study for subjects originally randomised to the darbepoetin alfa 20090160 study. Subjects must complete the 20090160 in order to be eligible for participation in this study, thus subjects will not be replaced.

3.5 Estimated Study Duration

3.5.1 Study Duration for Subjects

The maximum individual treatment duration for subjects that enter this companion study is approximately 73 weeks. The overall study duration is dependent upon the length of the enrollment period for the parent study (20090160).

3.5.2 End of Study

The study will end when all subjects complete the treatment period through week 73 and the End of Study (EOS) visit or are withdrawn from investigational product due to loss of response or disease progression or withdraw informed consent or die (see Section 8.3).

4. SUBJECT ELIGIBILITY

Investigators will be expected to maintain a screening log of all potential study candidates that includes limited information about the potential candidate (eg, date of screening). This log may be completed and updated via an Interactive Voice Response (IVR)/Interactive Web Response (IWR) system. Before any study-specific procedure, the appropriate written informed consent must be obtained (see Section 11.1).

| 4.1 | Inclusion Criteria |
|-------|---|
| 4.1.1 | General |
| 101 | Subject or subject's legally acceptable representative has provided informed consent prior to any study-specific activities/procedures being initiated; |
| 102 | Subject must continue LTFU within parent study (20090160); |
| 103 | Subject understands that darbepoetin alfa treatment will not be provided by Amgen past week 73; |
| 104 | Subject completes dosing in the active treatment period (through week 70 or week 71) and completed the end of the active treatment period (EOATP) visit of the parent study (20090160); |
| 4.1.2 | Disease-related |
| 105 | Subject must have an ongoing clinically relevant erythroid response as assessed by the Investigator using current response criteria (ie, IWG response criteria); |

Page 25 of 66

| | Darbepoetin alfa Jumber: 20130113 April 2013 Page 26 of 66 |
|-------|--|
| 4.2 | Exclusion Criteria |
| 4.2.1 | Disease-related |
| 201 | Transfusion dependence defined as receiving a total of ≥ 4 units of RBC transfusion in the previous 8-week period prior to enrolment; |
| 202 | Known diagnosis of acute myelogenous leukemia (AML) or marrow collagen fibrosis; |
| 203 | Known refractory anaemia with excess blast-2 (RAEB-2); |
| 204 | Known diagnosis of intermediate-2 or high risk MDS per IPSS; |
| 4.2.2 | Medications or Other Treatments |
| 205 | Subjects received thrombopoiesis-stimulating factors (eg, eltrombopag, romiplostim) in the MDS 20090160 study or planning to receive such agents during the study; |
| 206 | Subjects receiving any investigational agents/devices not currently approved by the country's regulatory authority for the indication of use. |

5. SUBJECT ENROLLMENT

Before subjects begin participation in any study-specific activities/procedures, Amgen requires a copy of the site's written independent ethics committee (IEC) approval of the protocol, informed consent form (see Section 11.2). Subjects must personally sign and date the IEC- and Amgen-approved informed consent form before commencement of study-specific procedures.

Each subject who enters into the screening period for the study will receive a unique subject identification (ID) number before any study-related activities/procedures are performed. The start of screening is defined when the subject signs of the informed consent form. The subject identification number will be assigned by the interactive voice response system (IVRS) and must remain constant throughout the entire clinical study. This number will be used to identify the subject throughout the clinical study and must be used on all study documentation related to that subject. Subjects that screen fail are not eligible for rescreening into the study. The site will be required to enter the subjects' ID number from the MDS 20090160 study into the IVRS.

A subject is considered enrolled when the investigator decides that the subject has met all eligibility criteria. The investigator is to document this decision and date, in the subject's medical record and on the enrollment electronic case report form (eCRF).

6. TREATMENT PROCEDURES

6.1 Classification of Product

The Amgen Investigational Product used in this study includes open-label darbepoetin alfa. The Investigational Product Instruction Manual (IPIM), a document external to this protocol, contains detailed information regarding the storage, preparation, and administration of darbepoetin alfa.

6.2 Investigational Product

6.2.1 Amgen Investigational Product

Darbepoetin alfa will be manufactured and packaged by Amgen Inc. and distributed using Amgen clinical study drug distribution procedures. The investigational product, darbepoetin alfa, is provided in single dose vials of human serum albumin-free polysorbate solution that is a clear, colorless, sterile, preservative-free protein solution. Each vial will contain 500 μ g, 300 μ g, 200 μ g, or 100 μ g of darbepoetin alfa per mL. For dose adjustment and stopping guidance, refer to Section 6.2.1.1. The dose, frequency, date of administration, box number of investigational product is to be recorded on each subject's eCRF.

The day of the first dose of IP (darbepoetin alfa) will be considered study day 1. Investigational product should be administered subcutaneously (SC) by the appropriately trained and designated study personnel at the dosing schedule outlined in the Schedule of Assessments (Table 5).

6.2.1.1 Dosage, Administration, and Schedule

Darbepoetin alfa will be open-label. The first dose and dosing frequency of darbepoetin alfa on day 1 / week 1 should carry forward from the last dose and frequency from the parent study (darbepoetin alfa MDS 20090160 study) administered at week 70 / 71. The day 1 / week 1 visit should align within +10 days of the EOATP visit at week 72 / 73 from the darbepoetin alfa MDS 20090160 study.

The dosing schedule is described by a schema in the protocol synopsis.

6.2.1.2 Dosage Adjustments, Delays, Rules for Withholding or Restarting, Permanent Discontinuation

There will be no interactive voice recognition system (IVRS) guidance for IP dosing in this protocol. The IVRS will only be used in this study to track IP supply to sites and will allocate a IP box number based on the IP dose information entered by the site.

Each subject entering the study will continue the last IP dose and frequency from the parent study (20090160). The investigator may choose to increase the dose of darbepoetin alfa with the maximum dose permitted of 500 µg Q2W. Dose increases should follow a step-wise approach, (eg, 300 µg to 500 µg; 200 µg to 300 µg) with at least 8 weeks at a given dose before the dose may be increased.

The frequency of darbepoetin alfa administration may also be changed, eg, from Q2W to Q3W dosing. No two Q3W or Q2W doses should be administered within any contiguous 14-day or 7-day period, respectively.

The Investigators should use their clinical judgment to assess the best dose and frequency considering risks and benefits, and subject needs. Adjustments to the darbepoetin alfa dose should be made based on the most recent local hemoglobin (Hb) value obtained within 1 day before the dosing visit. Dosing information and local Hb values will be recorded in the eCRF. The reason for a dose change is to be recorded on the eCRF.

Investigators should closely monitor each subjects' Hb values and suspend the dose of IP when the Hb exceeds the 12 g/dL threshold. IP should temporarily be withheld until Hb falls to ≤ 11.0 g/dL at which time IP may be restarted at a dose that is reduced from the previous dose (ie, 500 µg to 300 µg; 300 µg to 200 µg; 200 µg to 100 µg. Table 4 provides an outline of the recommended dose reductions.

Subjects will be permanently discontinued from darbepoetin alfa treatment and will complete the EOS visit at the next scheduled study visit if at any time the:

- subject loses erythroid response defined as Hb decrease of ≥ 1 g/dL compared to day 1 (Hb averaged over 8 weeks)
- subject becomes transfusion dependent defined as ≥ 4 units of RBC transfusion relative to previous 8 weeks prior to enrolment

| Dose | No Previous Dose Reduction | 1 Previous Dose Reduction | 2 Previous Dose Reductions | 3 Previous Dose Reductions |
|---------------|--|--|--|----------------------------------|
| 500 μg Q3W | IP Reinstated at / Reduced to 300 μg Q3W | IP Reinstated at / Reduced to 200 μg Q3W | IP Reinstated at / Reduced to 100 μg Q3W | IP Discontinued |
| 500 μg Q2W | IP Reinstated at / Reduced to 300 μg Q2W | IP Reinstated at / Reduced to 200 μg Q2W | IP Reinstated at / Reduced to 100 μg Q2W | IP Discontinued |

Table 4. IP Dose Reductions

Q3W = every 3 weeks; Q2W = every 2 weeks

Page 28 of 66

Page 29 of 66

A maximum of 3 dose reductions are permitted during the study. Should a subject meet the criteria for a fourth dose reduction, the subject will be permanently discontinued from IP treatment and will complete the EOS visit at the next scheduled study visit.

At any time during the study, the investigator may withhold or discontinue IP for any subject who experiences a severe or life-threatening adverse event. In the case of uncontrolled blood pressure, hypertensive crisis, or occurrence of thromboembolic event, the recommendation is for the investigator to withdraw the subject from IP. Investigational product must also be discontinued for a subject upon the investigator's determination of progression to AML, or diagnosis of new malignancy.

Subjects that are withdrawn from IP should complete the EOS visit approximately 3 weeks after the last IP dosing visit.

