Summary of Subject Eligibility Criteria: This study will enroll MDS subjects that have completed dosing in the active treatment period (up to week 70 or week 71) and the end of the active treatment period (EAOTP) visit of the Darbepoetin alfa MDS 20090160 study. Subjects must have an ongoing clinically relevant erythroid response at week 70 / 71 in the parent study (20090160) per the investigator clinical judgment. Subjects with MDS that have known progression to intermediate-2 or high risk per the MDS International Prognostic Scoring System (IPSS) are not eligible. Subjects who have progressed to acute myelogenous leukemia (AML) are not eligible. For a full list of eligibility criteria, please refer to Section 4.1 and Section 4.2.

Investigational Product

Amgen Investigational Product Dosage and Administration:

Eligible subjects will receive the first dose of subcutaneous (SC) darbepoetin alfa at the same dose that was last administered at the last dosing visit of the active treatment period in the darbepoetin alfa MDS 20090160 study (week 70 or week 71, depending on the dosing frequency in the active treatment period of the 20090160 study).

Investigators may elect to maintain subjects on the same dosing frequency or change the dosing frequency depending on erythroid response and Hb value (see Section 6.2.1.2).

Adjustment to the darbepoetin alfa dose will be made based on the most recent local laboratory Hb value obtained within 1 day before the dosing visit and taking into account transfusion information. Investigators should closely monitor Hb values and hold the dose of IP when the Hb exceeds the 12 g/dL threshold (refer to Section 6.2.1.2 for full dosing guidelines).

Procedures: Vital signs including blood pressure, local laboratory Hb, RBC transfusion data, and safety reporting will be performed at each visit. An end of study (EOS) visit will be performed at week 76, or 3 weeks after last dose of darbepoetin alfa for subjects who withdraw from the study earlier. For a full list of study procedures, including the timing of each procedure, please refer to Section 7 and the Schedule of Assessments (Table 5).

Page 3 of 66

Page 4 of 66

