7. STUDY PROCEDURES

7.1 Schedule of Assessments

| | Screen / Enroll | Active Treatment Period | End of Study ^g |
|--|---------------------------------|---|------------------------------|
| Study Week | 72 / 73 ^a / Day 1 | Q3W or Q2W dosing up to week 73 (Q3W) | 76 |
| Informed Consent | x | | |
| Medical history | x | | |
| Physical examination | x | | |
| Physical measurements (height and weight) ^b | x | performed at each visit | x |
| Vital Signs (heart rate, temperature, blood pressure) | х | performed at each visit | x |
| Assess for signs and symptoms of clinically relevant TVE | x | performed at each visit | x |
| Adverse Events (AEs), Serious Adverse Events (SAEs) ^C | x | performed at each visit | x |
| Key concominant medications, and red blood cell (RBC) transfusions | x | Assessed at each visit and throughout the study | |
| Local laboratory haemoglobin for dosing decision | x | performed at each visit | |
| IP (darbepoetin alfa) administration ^e | х | performed at each visit | |
| Darbepoetin alfa antibody sample collection | x ^f | | х |

Table 5. Schedule of Assessments

a. Last visit of the MDS 20090160 study at week 72 / 73 is the first dosing visit for 20130113.

b. Height only collected as part of screening. Weight collected at each visit.

c. AEs and SAEs will be reported throughout the study through 30 days after last dose of IP (darbepoetin alfa).

d. Dosing will occur Q3W ± 6 day or Q2W ± 6 days. No 2 Q3W or Q2W doses should be administered within any contiguous 14-day or 7-day period, respectively. Dosing decision based on local lab Hb taken within 1 day before IP dosing visit (See Protocol Section 6.2.1.2 for dosing guidelines).

e. Results of local laboratory Hb must be available and reviewed prior to IP adminstration.

f. A Day 1 antibody sample is not required if appropriately collected in the MDS 20090160 study at the End of the Active Treatment Period (EOATP) visit.

g. End of Study (EOS) visit at week 76 or 3 weeks after last dose of IP from Q3W or Q2W dosing for subjects that end IP early.

Page 33

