7.2 General Study Procedures

Refer to the Schedule of Assessments (Table 5) for an outline of the procedures required at each study visit. The investigator at each site is responsible for ensuring that all study procedures are performed as specified in the protocol.

Each subject or their legally authorised representative must personally sign and date the Amgen- / IEC-approved informed consent form (ICF) before any study-specific procedures are performed. The ICF may be reviewed and signed/dated within 8 weeks of the screening assessments.

Demographic data collection including sex, date of birth, age, race, and ethnicity will be collected in order to study their possible association with subject safety data.

Each study visit may occur over a 2 consecutive day period. Study assessments including local laboratory Hb testing may be performed up to 1 day prior to the day of IP administration. For each study visit, all study procedures should be performed prior to IP administration.

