7.2.7 Adverse Events Reporting

Adverse events that occur beginning on day 1 through the EOS visit will be reported using the applicable eCRF. All serious adverse events occurring from the date the subject signs the ICF through 30 days after the last dose of IP will be reported to Amgen.

Adverse events ongoing at the end of the parent study (20090160) will be carried forward to the eCRF of this study.

Refer to Section 9.2 for more detail on adverse events reporting.

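### Minor: Table 5 carries non-serious AE reporting to day 30 but protocol 7.2.7 and 9.2.1 stop it at EOS, and SAP 2.1 closes the TEAE window before the SAE window

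*Protocol*

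**What the plan says.** **End of AE collection.** Protocol 7.2.7 states: "Adverse events that occur beginning on day 1 through the EOS visit will be reported using the applicable eCRF". Section 9.2.1 sets the same end for events that do not meet serious criteria. Footnote c of Table 5 (section 7.1) instead states: "AEs and SAEs will be reported throughout the study through 30 days after last dose of IP (darbepoetin alfa"). For serious events, 7.2.7, 9.2.2, footnote c and SAP 2.1 all agree on 30 days after the last dose.

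**TEAE window.** SAP 2.1 defines a treatment-emergent AE by onset from study day 1 to EOS. A sub-bullet defines a treatment-emergent SAE by onset from consent to 30 days after the last dose. Subject incidence of TEAEs is the only endpoint (protocol 10.1.1, SAP 4.1.1).

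**EOS date.** Footnote g of Table 5 places the "visit at week 76 or 3 weeks after last dose of IP from Q3W or Q2W dosing for subjects that end IP early". Section 7.2.9 (early stops) and SAP 2.1 add ± 7 days. Section 6.2.1.2 has two rules. After a fourth dose reduction "the subject will be permanently discontinued from IP treatment and will complete the EOS visit at the next scheduled study visit", and the same timing applies to loss of response and to transfusion dependence. The section then closes with a general sentence that counts from the last dosing visit: "Subjects that are withdrawn from IP should complete the EOS visit approximately 3 weeks after the last IP dosing visit".

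**The concern.** A site working from the Schedule of Assessments would ask about non-serious AEs up to day 30. A site working from the AE sections would stop at EOS. The glossary ends the study for an individual at the final EOS visit, and Table 5 schedules no contact after it, so days between EOS and day 30 cannot be treated as ordinary on-study follow-up. Nothing ranks the two instructions.

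The SAP then treats the same days differently by seriousness. A non-serious AE collected under footnote c would not be a TEAE. An SAE would be treatment-emergent under its own definition, but its onset would lie outside the TEAE window as literally written.

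At stake is which late events are collected, and which appear in the primary-endpoint listing. Because EOS closes the AE and TEAE windows, any doubt about the EOS date also moves that boundary.

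**Working it through.** Days are counted from the last dose administered (day 0).

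**Inputs**
- EOS after an early stop: 3 weeks ± 7 days (protocol 7.2.9, SAP 2.1).
- Completers: dosing up to week 73, EOS at week 76 (Table 5).
- Footnote c end of reporting: day 30.
- Visit interval: 21 days (Q3W) or 14 days (Q2W), each ± 6 days (Table 5 footnote d).
- Haemoglobin is reviewed before each dose (Table 5 footnote e), so a stop can be recognised at a visit where no dose is given.

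**1. The plan's EOS figure**
- Nominal: 3 × 7 = 21. Window: 21 − 7 = 14 to 21 + 7 = 28.
- Completers on an unchanged schedule: Q3W 1 + 3 × 24 = week 73; Q2W 1 + 2 × 36 = week 73. EOS is (76 − 73) × 7 = day 21.

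**2. Gap between EOS and day 30**
- Nominal, including those completers: 30 − 21 = 9 days.
- Range: 30 − 28 = 2 to 30 − 14 = 16 days.

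Under the 3-week rule EOS always precedes day 30, so the gap is not an edge case.

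**3. An event with onset after EOS and by day 30**

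| Event | Collected under 7.2.7, 9.2.1, 9.2.2 | Collected under footnote c | TEAE (SAP 2.1, literal) | Treatment-emergent SAE (SAP 2.1) |
|---|---|---|---|---|
| Non-serious | No | Yes | No | Not applicable |
| Serious | Yes | Yes | No | Yes |

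**4. EOS date under the next-visit rule, nominal intervals, no hold**
- Q3W, stop recognised at an undosed visit on day 21: 21 + 21 = day 42 (36 to 48 with ± 6 days). That is 42 − 28 = 14 days past the window.
- Q2W, same situation: 14 + 14 = day 28, inside the window.
- Stop between visits: day 21 (Q3W) or day 14 (Q2W), inside.
- If the haemoglobin was drawn the day before, as section 7.2 allows ("Study assessments including local laboratory Hb testing may be performed up to 1 day prior to the day of IP administration"), and the dosing-day visit counts as the next visit, Q3W gives day 21 and there is no conflict.

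A prior hold pushes the date out: with one visit already held, 3 × 21 = day 63 for Q3W and 3 × 14 = day 42 for Q2W.

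**5. Proposed cutoff, max(EOS, 30)**
- EOS on day 14, 21 or 28 gives day 30.
- EOS on day 42 gives day 42; EOS on day 63 gives day 63.

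**The case against.** **Footnote c does not define treatment emergence.** This is right. It is a reporting rule, and SAP 2.1 alone sets the TEAE window. A reader might infer that Table 5 contradicts the SAP's TEAE definition, but it does not. Footnote c conflicts with 7.2.7 and 9.2.1, on non-serious AEs only. The mismatch in the SAP is a separate one, between its own TEAE and SAE windows.

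**The SAE sub-bullet may extend the TEAE definition for serious events.** It sits under the TEAE heading, so this reading is possible. The SAP does not state it, and it would leave non-serious events after EOS excluded. On either reading the SAE listing shows the event, so no SAE is lost.

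**A longer window for SAEs is a legitimate choice, and the smaller repair is to split footnote c.** Ending AEs at EOS and SAEs at day 30 in the footnote would remove the conflict within the protocol. It would not settle whether a late SAE belongs in the primary-endpoint listing.

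**Section 6.2.1.2 need not contradict itself on EOS.** A reader might infer that it does. Its closing sentence counts from the last dosing visit, not the last dose. If the undosed day-21 visit is taken as that dosing visit, 21 + 21 = day 42, which matches the next-visit rule. The next-visit clauses also attach to three named stops and can be read as specific exceptions. What remains is a tension with the last-dose wording in the synopsis, footnote g, 7.2.9 and SAP 2.1, confined at nominal intervals and without a hold to the one Q3W case.

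**Conclusion.** The AE-window point stands as a minor error in the text. Sites have two end dates for non-serious AEs, 9 days apart nominally (2 to 16), and the SAP's two windows can put an SAE in one listing and leave it out of the listing for the only endpoint. These figures assume EOS falls on days 14 to 28. A completer whose last dose came before week 73, through a change of frequency or a hold, would have a different gap.

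The consequence is lines in listings. SAP 4.1.2 projects fewer than 10 subjects, plans no summary statistics and does not combine the data with the parent study. The documents do not support a claim that a safety estimate would be biased, or that serious events would go uncollected.

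The EOS date is a wording ambiguity only: day 42 against days 14 to 28 for a Q3W subject stopped at an undosed visit. It does not justify deleting the next-visit clauses, which would cost some subjects who have just lost response or become transfusion dependent a follow-up visit.

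**What to change.** In protocol 7.2.7, 9.2.1 and Table 5 footnote c, end AE collection at the later of EOS and 30 days after the last dose administered. Use the same cutoff for TEAEs in SAP 2.1. Leave the SAE window, the stopping rules and the next-visit clauses as they are.

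With this cutoff, no event up to the subject's EOS and no event within 30 days of the last dose is dropped, whichever EOS reading a site follows. The cutoff date can still differ in the one Q3W case (day 30 or day 42). A clarifying sentence in 6.2.1.2 on which rule governs that case would be optional.

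The cost is wording in both documents and a slightly longer follow-up. SAE reporting already runs to day 30, but that follow-up would also have to ask about non-serious AEs. This applies to nearly all subjects, because an EOS on days 14 to 28 falls before day 30 and Table 5 schedules no later contact.
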